## CONFIDENTIAL

205847 (TBEV POLYGELINE FREE-025 EXT:021)

Protocol Amendment 2 Final

Timepoint(s)	Year 11		Year 12		Year 13		Year 14		Year 15	
Type of contact	Visit 23.1	Visit 23.2	Visit 24.1	Visit 24.2	Visit 25.1	Visit 25.2	Visit 26.1	Visit 26.2	Visit 27.1	Visit 27.2
	ad hoc visit 6 months after scheduled visit 23	21 days after ad hoc visit	ad hoc visit 6 months after scheduled visit 24	21 days after ad hoc visit	ad hoc visit 6 months after scheduled visit 25	21 days after ad hoc visit	ad hoc visit 6 months after scheduled visit 26	21 days after ad hoc visit	ad hoc visit 6 months after scheduled visit 27	21 days after ad hoc visit
Sampling timepoint(s)		post-vacc								
Record any intercurrent medical conditions	•		•		•		•		•	
Recording of SAEs and pregnancies #	•	•	•	•	•	•	•	•	•	•
Recording of SAEs related to study participation, or to a concurrent GSK medication/vaccine	•	•	•	•	•	•	•	•	•	•
Study Conclusion										•

Note: Visits numbers are consecutive numbers from previous studies, timepoints are indicated starting after enrolment in study V48P7E1. Results of the immunogenicity testing will be checked yearly in order to establish if antibody titre is below 10; if below this value, the subject will be included in the sub-cohort of subjects who received a booster dose, and booster dose of vaccine will be offered).

# Will only be collected from subjects who received a second booster vaccination in this study, all SAEs will be collected for 1 month after vaccination.

LV: Last Visit. LTFU: Long-term follow-up.

Whenever possible the investigator should arrange study visits within the interval provided in [Table 6](#). Of note, Visit 23 is the baseline visit for this study and it will need to be considered as the driver for the calculation of the interval for all subsequent visits as highlighted in the grey shaded rows of [Table 6](#).

**Table 6 Intervals between study visits**

Interval	Optimal length of interval
Scheduled visits	
Visit 23→Visit 24	1 year
Visit 23 → Visit 25	2 years
Visit 24→Visit 25	1 year
Visit 23 → Visit 26	3 years
Visit 25→Visit 26	1 year
Visit 23 → Visit 27	4 years
Visit 26→Visit 27	1 year
Unscheduled visits*	
Visit 23→Visit 23.1	6 months
Visit 23.1→Visit 23.2	21 days
Visit 24→Visit 24.1	6 months
Visit 24.1→Visit 24.2	21 days
Visit 25→Visit 25.1	6 months
Visit 25.1→Visit 25.2	21 days
Visit 26→Visit 26.1	6 months
Visit 26.1→Visit 26.2	21 days
Visit 27→Visit 27.1	6 months
Visit 27.1→Visit 27.2	21 days

Note: visits out of range can lead to elimination from per protocol analyses.

\* Only subject with an NT antibody titre below 10 at a scheduled visit will receive 6 months later a booster vaccination (all .1 visits) and will have an additional blood draw 21 days after this vaccination (all .2 visits)..

## 5.6. Detailed description of study procedures

### Scheduled visits:

#### 5.6.1. Informed consent

The signed informed consent of the subject must be obtained before study participation. Refer to Section [5.1](#) for the requirements on how to obtain informed consent.

#### 5.6.2. Check inclusion and exclusion criteria

Check all inclusion and exclusion criteria as described in Sections [4.2](#) and [4.3](#) before enrolment.

#### 5.6.3. Collect demographic data

Record demographic data such as date of birth, sex and race in the subject's eCRF.

#### **5.6.4. Medical history**

Obtain the subject's medical history by interview and/or review of the subject's medical records and record any pre-existing conditions or signs and/or symptoms present in a subject prior to each visit as specified in [Table 4](#), in the eCRF.

#### **5.6.5. Physical examination**

Perform a physical examination of the subject, including assessment of oral body temperature and resting vital signs: systolic/diastolic blood pressure and heart rate prior to each visit as specified in [Table 4](#). Collected information needs to be recorded in the eCRF.

Treatment of any abnormality observed during physical examination has to be performed according to local medical practice outside this study or by referral to an appropriate health care provider.

The height of the subject will be measured at the first visit (Visit 23). The weight of the subject will be measured at all annual visits. The information will be recorded in the eCRF.

#### **5.6.6. Review of subject's continued eligibility**

At each annual study visit, review subject's continued eligibility in the study by checking inclusion/exclusion criteria.

If the subject is eligible to continue, study procedures are to be followed as outlined in [Table 4](#) and the next visit is to be scheduled.

#### **5.6.7. Sampling**

Refer to the Module on Biospecimen Management in the SPM for detailed instructions for the collection, handling and processing of the samples.

##### **5.6.7.1. Blood sampling for immune response assessments**

Blood samples will be taken during certain study visits as specified in Section [5.5](#) List of Study Procedures.

- A volume of at least approximately 10 mL of whole blood (to provide ca. 5mL of serum) should be drawn from all subjects included in the immunogenicity sub-cohort (Sub-cohort of subjects who received a second booster dose) for each analysis of humoral immune response at each pre-defined time point. After centrifugation, serum samples should be kept at -20°C/ -4°F or below until shipment. Refer to the SPM for more details on sample storage conditions.

**5.6.8. Check and record concomitant medication/vaccination and intercurrent medical conditions**

Concomitant medication/vaccination must be checked and recorded in the eCRF as described in Section [6.7](#).

Intercurrent medical conditions must be checked and recorded in the eCRF as described in Section [6.8](#).

**5.6.9. Recording of SAEs and pregnancies**

- Refer to Section [8.3](#) for procedures for the investigator to record SAE and pregnancies. Refer to Section [8.4](#) for guidelines and how to report SAE and pregnancy reports to GSK Biologicals.
- The subjects will be instructed to contact the investigator immediately should they manifest any signs or symptoms they perceive as serious.

**Unscheduled visits (For subjects with NT<10):****5.6.10. Check inclusion and exclusion criteria**

Refer Section [5.6.2](#).

**5.6.11. Medical history**

Obtain the subject's medical history by interview and/or review of the subject's medical records and record any pre-existing conditions or signs and/or symptoms present in a subject prior to each visit as specified in [Table 5](#), in the eCRF

**5.6.12. Physical examination**

Perform a physical examination of the subject, including assessment of oral body temperature and resting vital signs: systolic/diastolic blood pressure and heart rate at visits specified in [Table 5](#). Collected information needs to be recorded in the eCRF.

If the investigator determines that the subject's health on the day of vaccination temporarily precludes vaccination, the visit will be rescheduled.

Treatment of any abnormality observed during physical examination has to be performed according to local medical practice outside this study or by referral to an appropriate health care provider.

The weight of the subject will be measured and the information will be recorded in the eCRF at each vaccination visit.

### **5.6.13. Pregnancy test**

Female subjects of childbearing potential are to have a urine pregnancy test prior to any study vaccine administration. The study vaccine may only be administered if the pregnancy test is negative.

Note: Pregnancy test must be performed even if the subject is menstruating at the time of the study visit.

### **5.6.14. Check contraindications, warnings and precautions to vaccination**

Contraindications, warnings and precautions to vaccination must be checked at the beginning of the vaccination visit. Refer to Sections [6.5](#) and [6.6](#) for more details.

### **5.6.15. Assess pre-vaccination body temperature**

The oral body temperature of each subject needs to be measured prior to any study vaccine administration. If the subject has fever [fever is defined as temperature  $\geq 38.0^{\circ}\text{C}/100.4^{\circ}\text{F}$  regardless the location of measurement] on the day of vaccination, the vaccination visit will be rescheduled within the allowed interval for this visit (see [Table 6](#)).

### **5.6.16. Study group and treatment number allocation**

*Study group and treatment number allocation will be performed as described in Section [5.2](#). The number of the administered treatment must be recorded in the eCRF.*  
(Amended 23 February 2018)

### **5.6.17. Study Vaccine administration**

- After completing all prerequisite procedures prior to vaccination, if found eligible, one dose of study vaccine will be administered intramuscularly (IM) in the deltoid of the non-dominant arm (refer to Section [6.3](#) for detailed description of the vaccine administration procedure). If the investigator or delegate determines that the subject's health on the day of administration temporarily precludes vaccine administration, the visit will be rescheduled within the allowed time for this visit (refer to [Table 6](#) and [Figure 3](#)). The date of the administration of the vaccine should be recorded in the eCRF.
- The subjects will be observed closely for at least 30 minutes following the administration of the vaccine, with appropriate medical treatment readily available in case of anaphylaxis.

### **5.6.18. Sampling**

Refer Section [5.6.7](#).

**5.6.19. Check and record concomitant medication/vaccination and intercurrent medical conditions**

Refer Section [5.6.8](#).

**5.6.20. Recording of SAEs and pregnancies**

Refer Section [5.6.9](#).

**5.6.21. Study conclusion**

The investigator will:

- review data collected to ensure accuracy and completeness
- complete the Study Conclusion screen in the eCRF.

**5.7. Biological sample handling and analysis**

Please refer to the SPM for details on biospecimen management (handling, storage and shipment).

Samples will not be labelled with information that directly identifies the subject but will be coded with a unique sample identifier.

- Collected samples will be used for protocol mandated research and purposes related to the improvement, development and quality assurance of the laboratory tests described in this protocol. This may include the management of the quality of these tests, the maintenance or improvement of these tests, the development of new test methods, as well as making sure that new tests are comparable to previous methods and work reliably.
- It is also possible that future findings may make it desirable to use the samples acquired in this study for future research, not described in this protocol. Therefore, all subjects will be asked to give a specific consent to allow GSK or a contracted partner to use the samples for future research. Future research will be subject to the laws and regulations in Czechia and will only be performed once an independent Ethics Committee or Review Board has approved this research.

Information on further investigations and their rationale can be obtained from GSK Biologicals.

Any sample testing will be done in line with the consent of the individual subject.

Refer also to the Amendment 2 [Investigator Agreement](#), where it is noted that the investigator cannot perform any other biological assays except those described in the protocol or its amendment(s).

If additional testing is performed, the marker priority ranking given in Section [5.7.4](#) may be changed.

Collected samples will be stored for a maximum of 20 years (counting from when the last subject performed the last study visit), unless local rules, regulations or guidelines require different timeframes or different procedures, which will then be in line with the subject consent. These extra requirements need to be communicated formally to and discussed and agreed with GSK Biologicals.

### 5.7.1. Use of specified study materials

When materials are provided by GSK Biologicals, it is MANDATORY that all clinical samples (including serum samples) be collected and stored exclusively using those materials in the appropriate manner. The use of other materials could result in the exclusion of the subject from the per-protocol analysis (See Section 10.4 for the definition of analysis sets to be analysed). The investigator must ensure that his/her personnel and the laboratory(ies) under his/her supervision comply with this requirement. However, when GSK Biologicals does not provide material for collecting and storing clinical samples, appropriate materials from the investigator's site must be used. Refer to the Module on Clinical Trial Supplies in the SPM.

### 5.7.2. Biological samples

**Table 7 Biological samples**

Sample type	Quantity	Unit	Timepoint	Sub-cohort Name*
Blood	Approximately 10	mL	Visit 23, 24, 25, 26, 27	Cohort for persistence
Blood	Approximately 10	mL	Visit 23.2 or 24.2 or 25.2 or 26.2 or 27.2	Sub-cohort of subjects who received a second booster dose

\* Refer to Section 4.1 for sub-cohort description

### 5.7.3. Laboratory assays

Please refer to [APPENDIX A](#) for a detailed description of the assays performed in the study. Please refer to [APPENDIX B](#) for the address of the clinical laboratories used for sample analysis.

Antibodies against TBEV will be determined using a virus neutralisation test (NT). The assay will be performed at a GSK Biologicals' laboratory using standardised and validated procedures (refer to [Table 8](#)).

**Table 8 Humoral Immunity (Antibody determination) (Amended 23 February 2018)**

System	Component	Method	Kit / Manufacturer	Unit*	Cut-off*	Laboratory**
Serum	Anti TBE Antibody	NT	GSK Biologicals***	1/dilution	2	GSK Biologicals***

\* Assay cut-off and unit might be subject to change during the course of the study (e.g. in case of requalification, revalidation or standardization). In this case, this will be documented in the clinical report.

\*\*Refer to [APPENDIX B](#) for the laboratory addresses.

\*\*\* GSK Biologicals laboratory refers to the Clinical Laboratory Sciences (CLS) in Rixensart, Belgium; Wavre, Belgium; Marburg, Germany

Additional exploratory testing on the vaccine and/or on the disease under study may be performed within the framework of the study if deemed necessary for accurate interpretation of the data or should such assay(s) become available at GSK. These assays may not be represented in the objectives/endpoints of the study protocol.

The GSK Biologicals' clinical laboratories have established a Quality System supported by procedures. The activities of GSK Biologicals' clinical laboratories are audited regularly for quality assessment by an internal (sponsor-dependent) but laboratory-independent Quality Department.

#### 5.7.4. Biological samples evaluation

##### 5.7.4.1. Immunological read-outs

**Table 9      Immunological read-outs (Amended 23 February 2018)**

Blood sampling timepoint		Subset /Sub-cohort Name	No. subjects	Component	Components priority rank
Type of contact and timepoint	Sampling timepoint				
Visit 23	Year 11	All subjects	200	Anti TBE Antibody *	1
Visit 23.2	Year 11 + 6 months + 21 days	Subjects with second booster on Visit 23.1**	**	Anti TBE Antibody *	1
Visit 24	Year 12	All subjects	200	Anti TBE Antibody *	1
Visit 24.2	Year 12 + 6 months + 21 days	Subjects with second booster on Visit 24.1**	**	Anti TBE Antibody *	1
Visit 25	Year 13	All subjects	200	Anti TBE Antibody *	1
Visit 25.2	Year 13 + 6 months + 21 days	Subjects with second booster on Visit 25.1**	**	Anti TBE Antibody *	1
Visit 26	Year 14	All subjects	200	Anti TBE Antibody *	1
Visit 26.2	Year 14 + 6 months + 21 days	Subjects with second booster on Visit 26.1**	**	Anti TBE Antibody *	1
Visit 27	Year 15	All subjects	200	Anti TBE Antibody *	1
Visit 27.2	Year 15 + 6 months + 21 days	Subjects with second booster on Visit 27.1**	**	Anti TBE Antibody *	1

\*The results of this testing might potentially impact the subject medical care.

\*\*Only subject with an NT antibody titre below 10 at a scheduled visit will receive 6 months later a second booster vaccination and will have an additional blood draw 21 days after this vaccination.

### 5.7.5. Immunological correlates of protection

#### Neutralization assay:

The presence of circulating antibodies to the virus at or above locally agreed concentrations (for example, an NT titre of  $\geq 10$ , evaluated with the Holzmann NT, Vienna) is commonly considered to be a surrogate marker of protection [WHO, 2011b]. However, systematic clinical studies that substantiate this assumption are not available [WHO, 2011b].

According to the test procedure of the GSK Biologicals' NT, the lower limit for detectable neutralizing TBE antibodies is a titre of 2. The lower working range is defined by technical conditions, since the lowest starting dilution is a 1:2 dilution). In order to identify a clinically meaningful threshold of NT titre for GSK in-house NT, an evaluation of TBE NT antibody titres in 19 subjects with evidence for a naturally acquired TBE immunity was performed [Zent, 2004]. This approach was based on the following consideration: TBE disease is assumed to provide a life-long lasting immunity. That is, no reports of re-occurrence of TBE disease have been reported to date.

Therefore, it can be assumed that antibody titres in subjects with a naturally acquired TBE immunity, but without manifest TBE disease are clinically meaningful. Retrospective analysis of basic NT titres of 19 subjects who tested TBE NT positive prior to their 1st TBE vaccination revealed an NT titre of approximately 10 as a lower confidence limit of the GMT (NT). Therefore, a titre of 10 has been considered as a more conservative threshold than 2 for interpretation of results of the GSK Biologicals' in-house NT.

The investigator is encouraged to share the immunological assay results for non-responders with the study subjects/subjects' parent(s)/LAR(s).

For the subjects identified as non-responders, it remains the responsibility of the investigator in charge of the subject's clinical management to determine the medical need for re-vaccination and to re-vaccinate the subjects as per local/regional practices.

Note: Non-responders in this study refer to subjects with an NT antibody titre below 1:10. Subjects with an NT antibody titre below 10 at a scheduled visit will be offered another booster vaccination in this study. If the subject has an exclusion criterion against study vaccination, it remains the responsibility of the investigator in charge of the subject's clinical management to determine the medical need for re-vaccination and to re-vaccinate the subject as per local/regional practices outside the frame of the study.

The date of the administration of the booster dose of *Encepur Adults* has to be recorded in the eCRF. The investigator should inform the subjects of the post-booster antibody response. In case of a suboptimal response after the administered booster dose, the subject may receive another booster outside the scope of the study.

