  - Fever is defined as temperature  $\geq 38.0^{\circ}\text{C}$  /  $100.4^{\circ}\text{F}$ . The preferred location for measuring temperature in this study will be the oral cavity.
  - Subjects with minor illness such as mild diarrhea or mild upper respiratory tract infection without fever (oral temperature  $<38.0^{\circ}\text{C}$ ) may be vaccinated at the discretion of the investigator.
- Expected general decrease in immune response, (eg, those who had sustained major injury or undergone recent major surgical operations, were undernourished, or had disorders involving a decreased immune response).
- Organic brain disturbances, including seizure disorders.
- Progressive neurological disorders.
- Suffered febrile or afebrile convulsions.
- Serious chronic illness (such as insulin dependent diabetes, cancer, autoimmune diseases).
- History of any reaction or hypersensitivity likely to be exacerbated by any component of the vaccine or chemically related substances.
- Individuals who received any other vaccines within 14 days (for inactivated vaccines) or 28 days (for live vaccines) prior to vaccination in this study or who are planning to receive any vaccine within 28 days from the study vaccines.
- Pregnant.

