### **10.4. Analysis Sets**

Definition of populations:

- a. All Enrolled Population
- all subjects who:  
have signed an informed consent and have been enrolled
- b. Full Analysis Set-1 (FAS-1)/Modified Intention-to-treat-1 (MITT-1) population, Immunogenicity
- all subjects in the enrolled population who:  
provide at least one evaluable serum sample
- c. Full Analysis Set-2 (FAS-2)/Modified Intention-to-treat (MITT) population, Immunogenicity
- all subjects in the enrolled population who receive one booster dose during the trial and provide at least one evaluable serum sample after booster dose
- d. Per Protocol Set/ Per protocol-1 (PP-1) population, Immunogenicity
- all subjects in the FAS-1/MITT-1 Immunogenicity population who:  
provide evaluable serum samples at the relevant time points and have no major protocol violation as defined in the Statistical Analysis Plan (SAP).
- e. Per Protocol Set/ Per protocol-2 (PP-2) population, Immunogenicity
- all subjects in the FAS-2/MITT-2 Immunogenicity population who:  
provide evaluable serum samples after booster dose and have no major protocol violation as defined in the Statistical Analysis Plan (SAP).

A major deviation is defined as a protocol deviation that is considered to have a significant impact on the immunogenicity result of the subject.

Examples of major deviations would include:

- confirmed exposure to TBE (documented diagnosis of TBE infection) or other Flaviviruses,
- documented TBE or *Flavivirus* vaccination other than indicated during the course of the study.

The main populations for immunogenicity analyses will be the PPS. FAS will be supplied as sensitivity analyses.

Subjects lost to follow up after having received their first booster dose in the V48P7E1 study will not be part of any set of analysis.

f. Safety Population

- The safety population will include all subjects who will receive a booster vaccination in this study.

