## **10.5. Derived and transformed data**

- Immunogenicity

- The cut-off value is defined by the laboratory before the analysis and is described in Section 5.7.3.
- A seronegative subject is a subject whose titre is below the cut-off value.
- A seropositive subject is a subject whose titre is greater than or equal to the cut-off value.
- The GMTs calculations are performed by taking the anti-log of the mean of the log concentration/titre transformations. Values to be used for the antibody concentrations/titres below the assay cut-off will be described in the Statistical Analysis Plan (SAP).
- Handling of missing data: for a given subject and a given immunogenicity measurement, missing or non-evaluable measurements will be replaced only if values before and after are available. In such an occurrence, the following rule will apply:
  - The missing value will be imputed to be equal to the lowest one between the previous and the subsequent available values (conservative approach).
  - Subjects receiving a booster dose because their NT <10 will be kept in the analysis of persistence until year 15 with an NT imputed value equal to 1.

In case of significant non-compliance of study procedures for reporting symptoms, the analysis plan will be reassessed to ensure more accurate reporting of study data by further analysis.

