5. ANALYSIS SETS

5.1. Definition

Definition of populations:

- a. All Enrolled Population
- all subjects who:
have signed an informed consent and have been enrolled
- b. Full Analysis Set-1 (FAS-1)/Modified Intention-to-treat-1 (MITT-1) population, Immunogenicity
- all subjects in the enrolled population who:
provide at least one evaluable serum sample
- c. Full Analysis Set-2 (FAS-2)/Modified Intention-to-treat (MITT) population, Immunogenicity
- all subjects in the enrolled population who receive one booster dose during the trial and provide one evaluable serum sample after booster dose
- d. Per Protocol Set/ Per protocol-1 (PP-1) population, Immunogenicity
- all subjects in the FAS-1/MITT-1 Immunogenicity population who:
provide evaluable serum samples at the relevant time points and have no major protocol violation as defined in the Statistical Analysis Plan (SAP).
- e. Per Protocol Set/ Per protocol-2 (PP-2) population, Immunogenicity
- all subjects in the FAS-2/MITT-2 Immunogenicity population who:
provide evaluable serum samples after booster dose and have no major protocol violation as defined in the Statistical Analysis Plan (SAP).

A major deviation is defined as a protocol deviation that is considered to have a significant impact on the immunogenicity result of the subject.

Examples of major deviations would include:

- confirmed exposure to TBEV (documented diagnosis of TBEV infection) or other Flaviviruses,
- documented TBEV or *Flavivirus* vaccination other than indicated during the course of the study.

The main populations for immunogenicity analyses will be the PPS. FAS will be supplied as sensitivity analyses.

f. Safety Population

- The safety population will include all subjects who will receive a booster vaccination in this study.

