6.3. Immunogenicity**6.3.1. Analysis of immunogenicity planned in the protocol**

The primary analysis population for immunogenicity is the per protocol set and if, in any study group, the percentage of subjects with serological results excluded from the PP set is at least 10%, a second analysis will be performed on the FAS. All analyses entail the calculation of summary statistics by vaccination schedule and age stratification, together with their 95% confidence intervals.

Long-term immunogenicity (persistence).

- Percentages of subjects with neutralizing antibody titres ≥ 2 and ≥ 10 as measured by NT assay will be tabulated by vaccine schedule (as assigned from the parent study) together with the associated two-sided 95% Clopper-Pearson confidence intervals (CIs). The vaccine schedule difference in the percentage of subjects with neutralizing antibody titres ≥ 2 and ≥ 10 will be calculated using a binomial distribution. The associated confidence interval for these differences will be constructed using the Miettinen-Nurminen method.
- GMTs with the associated 95% CIs will be computed for each vaccine schedule (as assigned from the parent study), by taking the exponential of the corresponding log10-transformed (least squares) means and 95% confidence intervals, from an ANOVA model with group as fixed factor. Vaccine schedule differences along with 95% CIs will also be computed.

SAS code

The SAS statements to calculate the adjusted GMCs will be similar to:

```
PROC glm;  
  BY vaccinegroup;  
  CLASS group;  
  MODEL log_Ab=group;  
  LSMEANS group / tdiff stderr;  
RUN;
```

Between-group ratios of GMTs will be calculated by including additional SAS statements within PROC GLM, similar to:

```
ESTIMATE 'Group 1 - Group 2' group 1 -1;
```

Subjects with antibody levels below 10 at a given visit (and that will therefore receive a booster dose) will be kept in the analysis of persistence also for the subsequent years with a value imputed to half of the detection limit, i.e. 1.

Analyses will be conducted on the PPS-1 (and repeated on the FAS-1, if appropriate).

Immune response to booster dose (boostability):

- Percentages of subjects with neutralizing antibody titres ≥ 2 and ≥ 10 at 21 days after administration of the booster dose, as measured by NT will be tabulated by vaccine schedule (as assigned from the parent study) together with the associated two-sided 95% Clopper-Pearson CIs.

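### TBE vaccination outside the study after NT <10 may remove a persistence failure from PPS-1, while the same failure boosted in the study is kept; the plan does not settle which rule applies

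*Protocol*

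**What the plan says.** **Route after NT <10.** The study booster is offered to subjects below 10 at a scheduled visit. Protocol 4.3 adds exclusions that apply only to the booster, for example "Serious chronic illness (such as insulin dependent diabetes, cancer, autoimmune diseases". For a subject who meets one, Protocol 5.7.5 makes it the investigator's responsibility to judge the medical need and "to re-vaccinate the subject as per local/regional practices outside the frame of the study".

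**Who leaves PPS-1.** PPS-1 (Protocol 10.4, SAP 5.1) requires that there be no major violation. Among the examples of a major deviation, both documents list documented TBE or flavivirus "vaccination other than indicated during the course of the study". SAP 5.2.2.2 states that right censoring does not apply. Visit-level censoring in SAP 5.2.2.3 covers only the blood-sample schedule.

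**Who is kept as a failure.** Protocol 10.5: "Subjects receiving a booster dose because their NT <10 will be kept in the analysis of persistence until year 15", with NT set to 1. SAP 6.3.1, in line with Protocol 10.7.2: "Subjects with antibody levels below 10 at a given visit (and that will therefore receive a booster dose) will be kept in the analysis", with later years set to half the detection limit, i.e. 1.

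**Role of the FAS.** Protocol 10.4 and SAP 5.1 supply the FAS as a sensitivity analysis without condition. Protocol 10.7.1 and SAP 6.3.1 call for it only if at least 10% of subjects with serology in some group are excluded from the per-protocol set.

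**The concern.** The persistence rules assume that every subject below 10 then receives the study booster. The design does not guarantee this. General entry does not require good health, but the booster does, so the cohort can include subjects who may be followed but not boosted.

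If such a subject is vaccinated elsewhere and is then dropped as a major deviator, the reason for exclusion follows from the primary outcome: only a titre below 10 opens that route. The result below 10, validly measured before the outside dose, would go too, because no censoring rule preserves it. A subject with the same titre who can take the study booster remains a failure to Year 15. At stake are the percentage with NT ≥10 and the GMT in the main analysis set, the figures meant to inform the timing of the second booster.

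Leaving the point open has its own cost. The study is open-label and titres are listed each year (SAP 8.1), so the classification would be made by people who know the titres.

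**Working it through.** **Step 1: apply the passages to one subject (NT below 10, barred from the study dose, vaccinated outside).**

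| Text | Result |
|---|---|
| Major-deviation example (Protocol 10.4, SAP 5.1) | Plain wording: out of PPS-1; no exception for Protocol 5.7.5 |
| Protocol 10.5 | Keyed to a booster given because NT <10, not expressly the study booster: can be read as kept, NT = 1 |
| Protocol 10.7.2, SAP 6.3.1 | Keyed to a level below 10: can be read as kept, NT = 1 in later years |
| SAP 5.2.2.1, code 150/1040 | Needs a vaccine the protocol forbids. A licensed TBE vaccine is not on the all-subjects list in Protocol 6.7.2. The additional list for subjects needing a second booster mentions planned vaccines but does not say whether it reaches this dose |
| SAP 5.2.2.1, vaccination-error codes | Limited to boosters at ad hoc visits: do not apply |

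The same subject can be in or out, depending on the passage followed. The dose would normally be documented, since Protocol 5.5 (Table 4) and 6.7 ask about vaccinations at annual visits.

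**Step 2: direction.** Let N be the group size, F the number below 10 by Year 15, and L the number of those removed. The percentage with NT ≥10 is (N − F)/N if all are kept and (N − F)/(N − L) if L are removed. The second is larger whenever L > 0 and F < N. This holds from the failing visit onward. At earlier visits the subject was at or above 10, so removal there loses a success.

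**Step 3: illustration.** The plan states no figure to reproduce; it says that the number falling below 10 cannot be estimated. N = 200 is from Protocol Table 1 (51 + 46 + 103). F/N and L/F are assumptions. All 200 are taken as evaluable.

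| F | L = 10% of F | L = 30% of F | L = 50% of F | All kept |
|---|---|---|---|---|
| 20 (10%) | 180/198 = 90.9% | 180/194 = 92.8% | 180/190 = 94.7% | 180/200 = 90.0% |
| 40 (20%) | 160/196 = 81.6% | 160/188 = 85.1% | 160/180 = 88.9% | 160/200 = 80.0% |

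In R, with 5 failures of which 2 are removed, 41/46 = 89.1% becomes 41/44 = 93.2%.

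**Step 4: how far the conditional FAS rule protects.** These are the most exclusions that stay under 10%, with no other exclusions, and their effect if about 20% fail.

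| Group | Under 10% | Triggers FAS-1 | All kept | Removed |
|---|---|---|---|---|
| C | 5/51 = 9.8% | 6/51 = 11.8% | 41/51 = 80.4% | 41/46 = 89.1% |
| R | 4/46 = 8.7% | 5/46 = 10.9% | 37/46 = 80.4% | 37/42 = 88.1% |
| AC | 10/103 = 9.7% | 11/103 = 10.7% | 82/103 = 79.6% | 82/93 = 88.2% |

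Shifts of 8.7, 7.7 and 8.6 points could therefore pass without the FAS repeat. These are upper bounds for that scenario, not expectations.

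**Step 5: GMT.** Take C with F = 10 and L = 5, failures at 1 (all failing before Year 15), and an assumed GMT of 100 in the others. Then 100^(41/51) = 40.5 becomes 100^(41/46) = 60.6, a ratio of 1.50. With assumed GMTs of 50 to 200, the ratio is 1.41 to 1.59.

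**The case against.** The strongest reply is that exclusion is not established. The deviation text is a list of examples, and its key phrase, "vaccination other than indicated during the course of the study", is undefined. Since Protocol 5.7.5 itself provides for the outside dose, that dose may count as indicated. The operative code list has no clear entry for it, and neither keep-in rule is limited to the study booster. All of this stands, and it makes the finding a conflict between passages rather than a certain exclusion.

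A reader might also infer that subjects barred from the booster are sent for outside vaccination. The text does not support that: the investigator first judges medical need. Temporary bars lead to rescheduling. Some subjects, such as those on immune-modifying drugs, may leave the per-protocol set on other grounds (Protocol 6.7.2, 6.8).

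FAS-1 needs only one evaluable sample, so it retains these subjects. In the most extreme cell of Step 3, 20/200 are removed. At most 5 + 4 + 10 = 19 can go without a trigger, so FAS-1 would be produced there. This limits the harm in large cases but not in small ones, and only if the conditional rule governs. It is also unclear whether FAS-1 would use NT = 1 or the boosted titre for a subject vaccinated outside.

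A further tempting inference is that Protocol and SAP disagree about subjects below 10 who are never re-vaccinated. They do not: Protocol 10.7.2 and SAP 6.3.1 carry the same rule. The tension is inside the Protocol, between 10.5 and 10.7.2. It arises only because 10.5 is silent on unboosted subjects, and it affects only the years after the failing visit.

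**Conclusion.** The point holds as a conflict that should be resolved before the final analysis. On the plain wording of the deviation example, a failure vaccinated outside the study leaves PPS-1, and the exclusion depends on the primary outcome. On the keep-in rules, the same subject can stay at NT = 1. The exclusion reading raises PPS-1 persistence at the failing visit and after it.

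The size cannot be derived from the documents. If 10% of 200 fall below 10, the overstatement is 0.9 to 4.7 points when 10% to 50% of them are removed. If 20% fall below, it is 1.6 to 8.9 points. Nothing in the documents shows which share is realistic, and the lower end is small.

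The documents do not support the stronger statement that these failures definitely leave PPS-1. Comparisons are descriptive and no formal test is affected, so the consequence is a possibly flattering main estimate, not an invalid inference. Because a stated rule can cause it and a short wording change removes it, the sponsor should act.

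**What to change.** Change analysis wording only; no clinical rule is touched.

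1. In Protocol 10.4 and SAP 5.1/5.2.2, state that TBE vaccination after a recorded NT <10 in this study, given inside or outside it, is not a reason for elimination from PPS-1.
2. Align Protocol 10.5 with Protocol 10.7.2 and SAP 6.3.1: every subject below 10 at a scheduled visit stays in the persistence analysis with NT = 1 in subsequent years, whether boosted in the study, outside it or not at all. Remove the parenthesis that presumes a booster. Using observed titres for subjects who are never re-vaccinated would also be a single rule, but it departs from the one already stated and would make handling depend on a vaccination decision taken after the outcome.
3. Report, per schedule group, how many subjects below 10 were boosted in the study, outside it or not at all.
4. Present FAS-1 alongside PPS-1 in every case, and remove the 10% condition or the contrary statement.

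The cost is a protocol and SAP wording change and a short table, with no new data. The downside is that reported persistence may be slightly less favourable.
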